11.4 HUMAN FACTORS AND USABILITY ACCEPTANCE CRITERIA

Each use scenario and user documentation assessment test case will be attributed one of the following assessments for task success:

- Successful: User is able to complete the task safely and effectively.
- Difficulty: User is able to complete the task safely and effectively, but has significant hesitation or challenges while completing the task.
- Close Call: User is able to complete the task safely and effectively, but performs it in a way that presents the potential for user harm (i.e. near-miss).
- Unsuccessful (Use Error): User is unable to independently complete the task or does not complete the task safely and effectively. Includes instances in which users are unable to

complete the task and as a result require study moderator assistance are assessed as unsuccessful.

• Did Not Perform: User does not complete the task for safe and effective use of the device.

Any instance of study moderator assistance will be noted and assessed depending upon the extent of the assistance provided.

The COBSS Use FMEA (governs Acceptance Criteria for the COBSS Usability Validation Study. Each hazard-related use scenario observed during usability validation testing will be documented and assessed for risk acceptability as defined in the Use FMEA.

In the case that a hazard-related use scenario is concluded to have an acceptable risk profile per the Use FMEA, its associated test case is considered to "pass." In the case that a hazard-related use scenario is concluded to have an unacceptable risk profile per the Use FMEA, its associated test case is considered to "fail." In the case of a failed test case, further risk mitigation and usability evaluation would be required. In the case that further risk mitigation is not possible, a risk-benefit analysis would be documented.

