Guided Breath Test (GBT): a function in the BSA wherein the BSA prompts the user through the steps of submitting a breath test. Based on the user's adherence to the proper technique, the user is provided with a pass or fail. They may repeat this GBT as often as they like if additional education and reinforcement of the technique is desired.

Objective Data: Data collected through direct observation.

Subjective Data: Data collected through user feedback via comments, ratings, and assessments provided by participants.

Task: Action or set of actions performed by a user to achieve a specific goal.

Use Error: User action or lack of action that was different from that expected by the manufacturer and caused a result that (1) was different from the result expected by the user and (2) was not caused solely by device failure and (3) did or could result in harm. (Section 3.9, FDA Guidance 2016).

User: Person who interacts with (i.e., operates or handles) the COBSS.

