9.10 STUDY PERSONNEL

The following roles will be fulfilled by Carrot Sense employees and consultants during the study:

- Study Moderator Responsible for moderating the study, delivering instructions (as needed) and ensuring that participants progress from one use scenario to the next, and asking questions to probe about observed use errors and close calls.
- Study Facilitator Responsible for organizing the simulated environment, study articles, equipment, and required documentation (e.g. informed consent form, non-disclosure agreements).
- Study Observer(s) Responsible for taking notes during the study sessions and documenting key events of the study as they occur.
- Technical Support Responsible for troubleshooting system issues and recording bugs in the case there is a system issue during the study session.

Individuals fulfilling the roles will be recorded in the final Usability Validation Study Report.

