11.0 TECHNICAL APPROACH AND STUDY DESIGN

Each study session will have the following format:

- 1. Introduction
- Simulated Use
- 3. Performance Paired Breath Samples (performed during Use Scenarios; see section 11.1)
- 4. User Documentation Assessment
- 5. Subjective Feedback and Rating Scales

Following a brief introduction session, each participant will undergo a study session lasting about 90 minutes. The study session will comprise 8 individual use scenarios, comparative performance paired breath samples with the study device and predicate device, user documentation (User Manual, Quick Start Guide, and Reference Card) assessment, subjective feedback and rating scales. In addition to the subjective feedback obtained during the defined sections below, subjective feedback may be collected during the use scenarios and User Documentation assessment to inform root cause analysis.

The use scenarios included in the study consider inputs from risk management documentation (COBSS Use FMEA, to test mitigations to device use (operation) related hazards. Each use scenario is expected to take up to 5 minutes (most will take 2-3 minutes). The use scenarios are listed in Table 2.

The study session will be conducted as a simulated use study where each participant will have access to the study article, a smartphone of their choice (Apple Inc. iPhone or Android smartphone), and will be monitored while performing the use scenarios. Each use scenario is monitored for difficulties, close calls and use errors. The use scenarios will allow for a detailed and focused assessment of the different components of the COBSS set-up and use.

Table 2 . Use Scenarios for Usability Validation

ID	Use Scenarios
1	
2	
3	
4	
5	
6	
7	
8	

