11.1.9 Use Scenario 7: Set reminders for future breath tests

• Prompt:

Please set reminders to perform breath tests every 2 hours from 8am to 10pm.

- Tasks:
- o Access the BSA Settings Page
- Set time limits and frequency for reminders

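### Do the overlapping ratings Unsuccessful (Use Error) and Did Not Perform in Section 11.4 need a rule to separate them?

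*Combined protocol and SAP*

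**What the plan says.** Section 11.4 sets a single-choice scale: "Each use scenario and user documentation assessment test case will be attributed one of the following assessments for task success". The five ratings are Successful, Difficulty, Close Call, Unsuccessful (Use Error) and Did Not Perform.

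- The fourth applies when the "User is unable to independently complete the task or does not complete the task safely and effectively". The same bullet assigns to it any non-completion that leads to moderator assistance.
- The fifth reads: "Did Not Perform: User does not complete the task for safe and effective use of the device".

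Section 5.0 has its own definition of use error. It begins "User action or lack of action that was different from that expected by the manufacturer" and adds conditions, among them that the event "was not caused solely by device failure and (3) did or could result in harm".

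The monitoring and follow-up text speaks of use errors, close calls and difficulties. Section 11.0 says "Each use scenario is monitored for difficulties, close calls and use errors", and Section 9.10 makes the moderator responsible for "asking questions to probe about observed use errors and close calls". Section 11.4 leaves acceptance to the Use FMEA: a hazard-related scenario passes or fails according to whether its risk is acceptable there.

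**The concern.** A scale that allows one rating per test case should have categories that exclude each other. Both definitions here turn on the task not being completed. Neither says whether the task was attempted, declined, skipped or never presented. In Use Scenario 7 the prompt is "Please set reminders to perform breath tests every 2 hours from 8am to 10pm". A participant who never sets the reminders could be rated either way.

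The choice appears to matter because only the fourth rating is labelled a use error. Section 11.5 requires how-and-why questions for use errors and difficulties, and Section 12.3 requires their analysis in the report. If observers apply the rating names literally, the same omission could be questioned and analysed for one participant and passed over for another. With 70 participants and possibly several observers, the use-error tally and the input to the Use FMEA could then depend on who held the data sheet.

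**Working it through.** No calculation applies, and the plan states no figure on this point to reproduce. The check sets the definitions against the possible situations and then follows an undone task through the later steps.

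**Where the ratings collide**

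| Situation | Unsuccessful (Use Error) | Did Not Perform |
|---|---|---|
| Not completed, moderator assists | Yes, assigned expressly | Settled by that assignment |
| Finished, but not safely or effectively | Yes | Poor fit: the task was performed |
| Presented, left undone, no assistance | Yes | Yes |
| Never presented (unasked prompt, participant has left) | Poor fit | Suggested by the name only |

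The live overlap is the third row, so 2 of the 5 ratings fit one situation.

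**How often the later text names the rating**

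Sentences or bullets that name use errors for capture, follow-up or reporting:

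- Section 9.10: 1
- Section 11.0: 1
- Section 11.5: 2
- Section 12.2.1: 5
- Section 12.3: 3

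The total is 1 + 1 + 2 + 5 + 3 = 12. None of the 12 names Did Not Perform, and 3 of them add a wider term, *problem* or *problems*. The zero carries little weight, because these sentences were picked for naming use errors. The word *unsuccessful* is also confined to Section 11.4. The later sections use Section 5.0 vocabulary and do not cite rating names.

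**What happens to an undone task rated Did Not Perform**

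1. *Definition.* Under Section 5.0 a lack of action can be a use error, whatever box is ticked in 11.4. If its conditions are met, the 11.5 questions and the 12.3 analysis apply.
2. *Probing.* Section 12.2.1 has the moderator look for the root cause of a problem as well as a use error. Failing to do a requested task is naturally a problem.
3. *Before the participant leaves.* Section 11.5 has the team check all data sheets for completeness and seek clarification where needed.
4. *After the session.* Section 12.2.1 has observers and moderators meet, and allows ratings to be revised with a comment or log showing agreement.
5. *Report.* Section 12.3 asks for observations of task performance and for use problems, so non-completion falls within its scope.
6. *Acceptance.* Section 11.4 judges hazard-related scenarios by Use FMEA risk acceptability. No rating count or error-rate threshold appears in the visible text.

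An undone task can therefore be examined and reported under either rating. What can differ is the column in which it is counted.

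**The case for a change.** The strongest case for a change is that the usual rescue, reading Did Not Perform as not attempted, is absent from the text. It would not fully work either, because the second limb of Unsuccessful requires no attempt. Consensus re-rating is logged but has no stated criterion, and agreement without a rule does not guarantee the same answer each time. The term *problem* is undefined in Section 5.0. The repair would be cheap: some wording and no extra participants.

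The overlap and the missing criterion stand. Three parts of the case are weaker.

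- It cannot be said that every omission escapes the use-error label, since the overlap means an omission can equally be rated Unsuccessful (Use Error).
- The reminders example shows an ambiguous rating but no lost safety information. Section 7.8 makes reminders optional, and the visible text names no harm from leaving them unset.
- The absence of a rule is certain only for the visible text. Section 12.2.1 refers to predetermined criteria in Sections 11.1 and 11.4. Parts of 11.1 are blank in the public copy, and the data sheets and Use FMEA are not included.

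Cheapness alone does not justify an amendment. The boundary could reasonably be drawn at attempted versus not attempted, or at presented versus not presented. Writing one of these down would record a convention without changing a decision.

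**Conclusion.** The definitions overlap for a presented task left undone without assistance. This is loose drafting that the study team can settle sensibly at its post-session meeting. Its visible size is 2 of 5 ratings for one kind of event, with an effect on the task-rating tally only. No pass/fail threshold moves, and the performance comparison of the two devices does not use these ratings. The number of events cannot be estimated from the documents.

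The conclusion rests on two assumptions: that *use error* in the follow-up and reporting sections carries its Section 5.0 meaning, and that a requested task left undone is treated as a problem to be probed. Both are the natural reading. If either failed, some root-cause detail on omissions could be lost, but acceptance would still be decided through the Use FMEA. No change to the plan is needed.

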11.5 METHODS FOR CAPTURING USE ERRORS

During each study session, observer(s), and moderator(s) will observe for difficulties, use errors and close calls that could inform modifications to the COBSS Use FMEA. The study moderator will also ask probing questions, at the end of the session, to reveal close calls that were not conveyed through observation. All use errors and difficulties will be followed with questions to identify how and why the participant believes they occurred. New, unforeseen use-related hazards will be assessed for risk acceptability and added to the COBSS Use FMEA.

The study team will include subjective assessments by participants for any observed use-related issues that could potentially result in harm to the user.

Users will perform tasks independently and in a natural manner, without guidance, coaching, praise, or critique from the test facilitator or moderator. Users will not be allowed a "second chance" to perform a task correctly after a failure. That is, if an irreversible safety or efficacy issue is observed in which a user would not normally have a "second chance" to resolve the issue, then any subsequent attempts to compete the task will serve as input only for continuous usability improvement purposes.

The study team will ensure participant feedback is documented throughout the session, as well as any protocol deviations. Prior to the end of the test session, the study team will review all data sheets for completeness and pursue additional information or clarification as needed. The study team will then inform participants when the test session is complete.

The study team will scan the data sheets and save them to a secure study file. All members of the study team will be familiar with the device operation to be qualified to administer the test and assess participant performance with the device. The study team will write the summary report.

12.0 STUDY RESULTS

12.1 DATA COLLECTION AND CONFIDENTIALITY

Subjects will be assigned a unique subject ID which will be used for data collection. Data collection will take place on paper or electronic case report forms (CRF) completed by the study team and study subjects. CRFs will be reviewed by the study team prior to the end of the study session to ensure completeness and then stored in a secure filing cabinet at the end of the day with access limited to necessary study personnel. Study data will be kept in a secure database by the investigator. This database will be accessible only by necessary study personnel. The database will not contain personal identifying information; all subject data in the database will be associated with study identification numbers. The data will be kept for 5 years.

12.2 ANALYSIS

The study will utilize paper-based data entry procedures, subject to audit per Carrot Sense standard operating procedures.

12.2.1 Human Factors and Usability

The data sheets will be printed and used to facilitate note taking and the capture of close calls and use errors that are observed during each session. Data collection and analysis will include both objective data and subjective data collected via test cases that are provided to the user.

Objective data will include:

- Participant answers to use scenarios and user documentation assessment test case questions assessing user comprehension.
- Study team assessment by use scenario, based on pre-determined acceptance criteria (see sections 11.1 and 11.4)

Subjective data will include:

- Participant feedback on ease of use, understandability, and possible improvements.
- Study team feedback on any issues with participant comprehension or ability to complete user tasks.

In the case that a problem or a use error is observed, the study moderator will probe for root cause and record the participant's assessment of safety and risk acceptability. This subjective input of risk acceptability will inform the final assessment and conclusion of risk acceptability made by the study personnel during data analysis. Both observational data and subjective input will facilitate identification and understanding of the root causes of use errors or difficulties that occur.

As needed, photo and video recordings may be implemented during the study to facilitate post-study analysis of user-feedback, use errors, and close calls.

More than one study observer may record data using the data sheets. As a result, data may differ between note-takers. After the session is complete, the observer(s) and moderator(s) will meet to discuss any difficulties, use errors, or close calls. Data will be compiled in a spreadsheet, and

study team may re-assess ratings based on further analysis, video review, or discussion (e.g. a "Difficulty" may be re-assessed as a "Close Call" after the data sheets are complete). Handwritten data will not require amendment based on the re-assessment. In any instances where ratings are modified, a comment will be made in the cell in the spreadsheet or a log will be otherwise recorded to indicate that each change was agreed upon by the study personnel.

12.2.2 Performance

See Sections 9.4 and 9.5 for statistical methodology. A paired breath sample is defined as subject submitting a breath sample unassisted using the study device, waiting 3-5 minutes, and submitting a breath sample assisted by a health care professional (or test administrator) using the predicate device.

A final report will be created to capture the results and analyses of the findings.

12.3 REPORT

A final report will be issued upon completion of testing and will include the following:

- Report must include observations of task performance and occurrences of use errors, close calls, and use problems.
- Report must include feedback from interviews with test participants regarding device use, use errors and problems (as applicable).
- Report must include description and analysis of all use errors and difficulties that could cause harm, root causes of the problems, and implications for additional risk elimination or reduction.
- Report must include testing details such as description of products tested and identification numbers.
- Report must identify staff members who tested and evaluated/inspected samples. Test date(s) must be identified.
- Report must identify any deviation from the protocol, and any anomalies in sample testing. Justification and approval of deviation by Carrot Sense must be documented.
- Report must include test results section and must identify any changes to the testing samples.
- Report must reference completed data sheets. All data sheets will be signed and dated.
- Report must be signed by the primary investigator or study team designee. It must also be reviewed and approved by the study team.

12.4 DEVIATIONS FROM PROTOCOL

[figure not shown]
To be determined by the study team during usability study. Deviations will be assessed through a consensus review of the study team. All deviations will be identified, recorded and analyzed in the final report.

14.0 RECORD RETENTION

Record keeping is performed in accordance with the SOP Control of Quality Records, SOP-1068.

